Nitazoxanide, in addition to antiparasitic activity, has broad-spectrum in vitro antiviral activity against influenza, RSV, norovirus, rotavirus, and hepatitis B and C viruses and has shown In vitro activity against MERS-CoV and other corona viruses.¹⁴ Clinical results for treatment of viral infections have been mixed. In one phase 2b/3 clinical trial, oral administration of nitazoxanide 600 mg twice daily for five days reduced the duration of clinical symptoms and reduced viral shedding compared to placebo in patients with influenza.³⁴ However, in a phase 2 study of nitazoxanide + SOC in patients with severe acute respiratory illness (SARI), nitazoxanide did not reduce the duration of hospital stay, supplemental oxygen use, or shedding of respiratory viruses on day 3 in patients with SARI.³⁵

Nitazoxanide is generally well tolerated. In the study by Haffizulla et al., adverse events were similar between groups, the most common being headache reported by 24 (11%) of 212 patients enrolled in placebo group, 12 (6%) of 201 patients in the nitazoxanide low-dose group, and 17 (8%) of 211 patients in the nitazoxanide high-dose group, or diarrhea, reported by seven (3%) patients in the placebo group, four (2%) patients enrolled in the nitazoxanide low-dose group, and 17 (8%) patients in the nitazoxanide high-dose group.³⁴ Similar safety and tolerability was seen in the study by Gamiño-Arroyo et al which reported the similar frequency of adverse events between nitazoxanide and placebo, the most common being gastrointestinal disorders (31.9%), infections and infestations (16.3%) and respiratory and thoracic disorders (16.3%).³⁵

The pharmacokinetics of hydroxychloroquine, ribavirin, and nitazoxanide are summarized below.

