 Adverse Events Based on Signs and Symptoms When collecting AEs, the recording of diagnoses is preferred (when possible) to recording a list of signs and symptoms. However, if a diagnosis is known and there are other signs or symptoms that are not generally part of the diagnosis, the diagnosis and each sign or symptom will be recorded separately.

D. Data Points

Case Report Forms

Completion of the electronic case report forms (eCRFs) will be done in accordance with the instructions outlined in the study specific data capture plan. All eCRFs are considered the primary

data collection document for the study and are stored in REDCap in a confidential format. Only key personnel who are delegated in the delegation of authority log are permitted to make entries, changes, or corrections in the eCRF. All users will complete user training, as required or appropriate per regulations. An audit trail will be maintained automatically by the electronic CRF management system.

Data Points to be collected:

- Baseline medical history
- Treatment compliance
- Daily temperatures
- Symptoms of disease
- Adverse events
- Concomitant medications
- Any standard of care treatments or procedures to manage COVID-19
- Viral load from saliva specimen
- Viral load from mid-turbinate self-nasal swab
- SARS-CoV-2 infections confirmed or suspected in household members

Data Submission Timeline and Forms

Completion of eCRFs will occur within 72 hours of study time point unless otherwise indicated. Baseline (pre-study) eCRFs (e.g., enrollment, medical history, concomitant medications, etc.) will be completed no later than 24 hours after the start of treatment.

E. Study Duration

Study participants will be treated for five (5) days and will then remain on follow-up for up to 28 days after entry into the study. The estimated time to complete the entire study including data analysis is 3-6 months

F. Endpoints

Primary endpoint:

1. Rate of decline in viral load over the 10 days after randomization

Secondary:

- 1. Proportion of participants with virus below LLOQ at day 10
- 2. Proportion of participants asymptomatic at day 10.
- For those who were asymptomatic at baseline: Progression to symptoms--presence or absence of key symptoms: fever ≥ 100.4^o F (38 ^o C); sore throat, cough, shortness of breath, myalgias, vomiting or diarrhea, or change in smell or taste

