Uncommon: ≥ 0.1 and < 1 %: Maculopathies, which may be irreversible. Retinopathy with changes in pigmentation and visual field defects (see Warnings and Precautions, Ophthalmologic). In its early form it appears reversible upon discontinuation of the drug. If allowed to develop however, there may be a risk of progression even after treatment withdrawal. Patients with retinal changes may be asymptomatic initially, or may have scotomatous vision with paracentral, pericentral ring types, temporal scotomas, abnormal color visions, reduction in visual acuity, night blindness, difficulty reading and skipping words. Corneal changes including edema and opacities. They are either symptomless or may cause disturbances such as halos around lights especially at night, blurring of vision, vision disturbances, or photophobia. They may be transient or are reversible upon discontinuation of therapy (see Warnings and Precautions, Ophthalmologic). *Not known*: Macular degeneration, which may be irreversible.

Gastrointestinal disorders

Very common: \geq 10 %: Abdominal pain, nausea. Common: Diarrhea, vomiting. These symptoms usually resolve immediately upon reducing the dose or upon stopping the treatment.

• Hepatobiliary disorders

Uncommon: ≥ 0.1 and < 1 %: Abnormal liver function tests. Not known: Fulminant hepatic failure (see Warnings and Precautions, Hepatic/Biliary/Pancreatic).

Immune system disorders

Not known: Urticaria, angioedema, bronchospasm.

• Metabolism and nutrition disorders

Common: \geq 1 and <10 %: Anorexia (usually resolves immediately upon reducing the dose or upon stopping the treatment). Not known: hypoglycemia (see Warnings and Precautions, Endocrine and Metabolism). Hydroxychloroquine may exacerbate porphyria (see Warnings and Precautions, General).

• Musculoskeletal and connective tissue disorders

Uncommon: ≥ 0.1 and < 1 %: Sensori motor disorders. Not known: Skeletal muscle palsies or skeletal muscle myopathy or neuromyopathy leading to progressive weakness and atrophy of proximal muscle groups. Depression of tendon reflexes, abnormal results of nerve conduction tests. Myopathy may be reversible after drug discontinuation, but recovery may take many months (see Warnings and Precautions, Musculoskeletal).

• Nervous system disorders

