During combination therapy for up to 48 weeks with peginterferon alfa-2a plus Ribavirin, growth inhibition was observed in pediatric participants 5 to 17 years of age. Decreases in weight for age z-score and height for age z-score up to 48 weeks of therapy compared with baseline were observed. At 2 years post-treatment, 16% of pediatric participants were more than 15 percentiles below their baseline weight curve and 11% were more than 15 percentiles below their baseline height curve.

The available longer term data on participants who were followed up to 6 years post-treatment are too limited to determine the risk of reduced adult height in some patients.

NITAZOXANIDE Adverse Events

Gastrointestinal

Gastrointestinal side effects have included abdominal pain (6.6% to 7.8%), diarrhea (2.1% to 4.2%), and nausea (3%). Side effects occurring in less than 1% of patients have included vomiting, anorexia, flatulence, dyspepsia, constipation, dry mouth, and thirst.

The incidence of gastrointestinal side effects may be dose related. Abdominal pain, diarrhea and discolored urine occurred more often in participants receiving higher doses (1 gram twice daily).

Nervous system

Nervous system side effects have included headache (3.1%). Dizziness, somnolence, insomnia, tremor, and hypesthesia have been reported by less than 1% of the patients.

Other

Adverse effects affecting the body as a whole have included asthenia, fever, pain (pelvic/back), flu syndrome, earache, and chills in less than 1% of patients.

Metabolic

Metabolic side effects have included increased creatinine and SGPT in less than 1% of patients.

Dermatologic

Dermatologic side effects have included pruritus, rash, and sweat in less than 1% of patients.

Ocular

Ocular side effects have included pale yellow eye discoloration (<1%).

Respiratory

Respiratory side effects have included epistaxis, rhinitis, lung disease, and pharyngitis.

Genitourinary

Genitourinary side effects have included discolored urine, dysuria, amenorrhea, metrorrhagia, and edema labia.

General

In general, side effects have been mild and transient in nature. The most frequent side effects have included abdominal pain, diarrhea, vomiting, and headache, and the rates of occurrence were not significantly different from placebo.

Musculoskeletal

Musculoskeletal side effects have included myalgia, leg cramps, and spontaneous bone fracture.

Cardiovascular

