6.0 Data Management Plan

6.1 Data Analysis

We will follow intention-to-treat principles and analyze the groups as randomized. A summary table of baseline variables will be created with means and standard deviations for continuous variables or percentages for categorical variables, all stratified by treatment group.

Primary outcome. We will have repeated measures of log10 VL for each participant. These measurements will occur on day 0 (baseline) and at about days 3, 6 and 10. We will fit a linear mixed effects model, where log10 VL is the outcome, indicators for treatment group (SoC reference), time, and treatment by time interactions are the predictors. The model will include a random slope and intercept, to account for within participant correlation. The robust sandwich variance will be used to estimate standard errors. Because we are estimating within participant changes over time from randomization, we can estimate a treatment effect at any particular day. Our primary hypotheses involve the change over time, which we will assess with the treatment by time interaction terms. If participants drop out from the study

before the day 10 visit, we will use all of their preceding data. Linear mixed effects models rely on the assumption that missing data are missing at random.

Secondary outcomes. For binary outcomes, such as progression to having symptoms, intubation, death, hospitalization, and admission to intensive care unit, we will fit logistic regression models. The covariates will include the treatment group indicators. We will report odds ratios and 95% confidence intervals. For change variables, such as change in viral shedding or change in Q-T interval, we will fit linear mixed effects models (similar to primary outcome).

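### Secondary endpoint 3 counts vomiting or diarrhea as COVID-19 progression with no attribution rule, so any net excess of these side effects on active drug would bias the comparison against treatment

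*Combined protocol and SAP*

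**What the plan says.** Section 1.3 F, secondary endpoint 3, applies to participants asymptomatic at baseline and records the presence or absence of key symptoms: fever of at least 100.4 °F, "sore throat, cough, shortness of breath, myalgias, vomiting or diarrhea, or change in smell or taste". It does not ask for a second symptom, for attribution to COVID-19, or for adjudication.

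Section 6.1 treats the result as a single yes/no outcome: "For binary outcomes, such as progression to having symptoms, intubation, death, hospitalization, and admission to intensive care unit, we will fit logistic regression models". On the model terms it says only "The covariates will include the treatment group indicators". It plans no analysis that sets gastrointestinal symptoms aside.

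The protocol describes the same symptoms as drug effects:
- Hydroxychloroquine (Section 4.7 A). The entry in the common category, defined there as at least 1% and below 10%, reads "Diarrhea, vomiting. These symptoms usually resolve immediately upon reducing the dose or upon stopping the treatment".
- Nitazoxanide (Section 4.7 A). "Gastrointestinal side effects have included abdominal pain (6.6% to 7.8%), diarrhea (2.1% to 4.2%), and nausea (3"%); vomiting is put below 1%. The section adds "Abdominal pain, diarrhea and discolored urine occurred more often in participants receiving higher doses (1 gram twice daily"), but also says that the rates of the most frequent side effects, diarrhea and vomiting among them, did not differ significantly from placebo.
- Cited influenza trial (Section 1.2). Diarrhea occurred in 7 of 212 on placebo (3%), 4 of 201 on low-dose nitazoxanide (2%) and "17 (8%) patients in the nitazoxanide high-dose group" (of 211).

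Treatment lasts 5 days (Section 1.3). Symptom questionnaires are completed daily for 10 days and on day 28, and also ask about reactions to study medication (Section 1.9). Grade 1 and 2 adverse events need not be recorded (Section 1.3 C).

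**The concern.** The natural reading of a presence-or-absence endpoint with an either/or list is that one listed symptom is enough. A baseline-asymptomatic participant whose only symptom is drug-induced diarrhea on day 2 then counts as having progressed to symptomatic COVID-19. If that happens more often on active drug, misclassification differs by arm and the endpoint mixes efficacy with tolerability. A real benefit would be diluted, and a null effect could look like mild harm.

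Masking does not prevent this. It stops knowledge of assignment from influencing reports, but the extra events are real symptoms that the definition counts. Adverse-event data will not separate them either, because mild events need not be recorded. The questionnaire's drug-reaction item could help, but no rule links it to the endpoint.

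**Working it through.** **1. The protocol's own rates.** 7/212 = 3.3%, 4/201 = 2.0% and 17/211 = 8.1%, which round to the stated 3%, 2% and 8%. The high-dose excess over placebo is 8.06% − 3.30% = 4.8 points (Fisher exact p = 0.037). Pooling the nitazoxanide arms gives (4 + 17)/(201 + 211) = 21/412 = 5.1%, an excess of 1.8 points. These are the only placebo-controlled diarrhea rates in the documents.

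**2. Model.** Let p be the true risk of COVID-19 symptoms and g the chance of vomiting or diarrhea from any other cause, assumed independent. Then

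observed risk = 1 − (1 − p)(1 − g).

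The documents give no value for p. The figures below assume it.

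**3. No true effect, p = 30% in both arms (assumed).**

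| g active vs placebo | Source | Observed active | Observed placebo | Odds ratio |
|---|---|---|---|---|
| 2% vs 3% | low-dose arm | 1 − 0.70 × 0.98 = 31.4% | 1 − 0.70 × 0.97 = 32.1% | 0.97 |
| 5.1% vs 3.3% | both arms pooled | 1 − 0.70 × 0.949 = 33.6% | 1 − 0.70 × 0.967 = 32.3% | 1.06 |
| 8% vs 3% | high-dose arm | 1 − 0.70 × 0.92 = 35.6% | 32.1% | 1.17 |
| 17% vs 3% | high dose plus top of hydroxychloroquine band | 1 − 0.70 × 0.83 = 41.9% | 32.1% | 1.53 |

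With exact counts instead of rounded percentages, the high-dose row gives 1.16. The last row takes 1 − 0.92 × 0.90 = 17%. It uses the upper limit of a label band, not placebo-subtracted, against a placebo rate for diarrhea only, so it is an upper scenario and not an estimate.

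**4. True benefit, 40% on placebo and 20% on active (assumed).** At 8% vs 3%, observed risks are 1 − 0.60 × 0.97 = 41.8% and 1 − 0.80 × 0.92 = 26.4%, so the 20-point difference becomes 15.4. At 5.1% vs 3.3% it is 42.0% − 24.1% = 17.9. Equal background rates of 3% would already reduce it to 41.8% − 22.4% = 19.4, so not all of the loss is due to the drug.

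**5. How many participants.** The number asymptomatic at baseline is not stated. With p = 30% and a net excess of 4.8 points, expected false progressions on active drug are n × 0.70 × 0.0475: about 0.3 for n = 10, 0.6 for n = 18, and 1.2 if all 35 in the arm were asymptomatic.

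**6. Power.** In that last, most favourable case (35 per arm), with 30% progression on placebo and a true odds ratio of 0.50, power is about 22.5% without the bias and 12.3% with a 4.8-point net excess.

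**The case against.** The strongest reply is that the documents do not establish an excess. Low-dose nitazoxanide had less diarrhea than placebo. Section 4.7 reports no significant difference from placebo, and Section 1.2 describes adverse events as similar between arms in both nitazoxanide trials it cites. The hydroxychloroquine frequencies are label bands without a comparator. The statement about 1 gram twice daily may not apply: Section 1.3 A gives two 250 mg nitazoxanide tablets twice daily and then describes the tablet as 500 mg, and those passages must be reconciled before its relevance can be judged. All of this stands. It limits the size and certainty of the bias, but not its direction if an excess occurs, and Section 1.7 says there are no data on the three drugs together.

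Second, counting every symptom whatever its cause is a defensible choice in a masked trial. Toxicity is a separate endpoint (secondary 6), and Objective 3 leaves room for symptom-by-symptom reporting. That is why the listed definition should stay. None of it says how the single binary result would be interpreted.

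Third, the bias works against the drug, so it is conservative for a claim of benefit. This also stands: there is little reason to make a favourable claim depend on the companion analysis.

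A reader might infer that the endpoint is certainly biased, or that an ineffective regimen would appear to worsen disease. The documents do not support either. The placebo-controlled rates range from no excess to 4.8 points, and even 4.8 points means about one extra event or fewer on active drug.

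**Conclusion.** The point holds as a conditional one. Endpoint 3 has no rule to keep drug-induced vomiting or diarrhea from counting as progression, the protocol names both as effects of study drugs, and any net excess on active drug would move the comparison against treatment.

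The size is open. With 30% true progression assumed in both arms and gastrointestinal events independent of disease, the odds ratio is about 1.06 from the pooled nitazoxanide arms and about 1.17 from the high-dose arm. Larger values require label rates that are not placebo-subtracted. The reading that one symptom is enough is the natural one but is not written out.

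This is a minor improvement to a secondary endpoint that has low power even without the bias. The primary viral-load endpoint is not affected.

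**What to change.** Keep the listed definition of endpoint 3 and add to Section 6.1:

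- A pre-specified companion analysis, using the same model and the same reporting period, in which vomiting or diarrhea with no other listed symptom does not count as progression. Present it beside the main result. Consult it in particular before concluding that treatment has no effect on progression or worsens it.
- A table of vomiting and diarrhea by arm, taken from the daily questionnaires. The adverse-event records will not serve, because grade 1 and 2 events need not be recorded.

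The cost is a few sentences of analysis-plan text and no new data collection, provided the questionnaire records these symptoms separately. The downside is that a few true COVID-19 cases with only gastrointestinal symptoms will not be counted in the companion analysis. Because the main analysis stays as written, those cases are still reported there. Fixing the rule before unblinding also avoids a later exclusion that would look driven by the data.

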1.0 Research Design

1.1 Purpose/Specific Aims

The purpose of this study is to evaluate the efficacy of Nitazoxanide (NTZ), Ribavirin (RBV) and Hydroxychloroquine (HCQ) versus placebo in participants with proven SARS-CoV-2 infection who are asymptomatic or mildly symptomatic with COVID-19. Those with illness requiring hospitalization, or who present with hypoxia (PO2<92%) or shortness of breath at time of enrollment are excluded.

A. Objectives

In participants with proven SARS-CoV-2 infection who are asymptomatic or mildly symptomatic with COVID-19 randomly allocated to nitazoxanide, ribavirin plus hydroxychloroquine (NTZ, RBV + HCQ) or placebo.

Primary Objective:

To assess the rate of decline in viral load over the 10 days after randomization between participants treated with NTZ, RBV + HCQ for COVID-19 and placebo.

Secondary Objective:

- 1. To compare the proportion of participants with virus below LLOQ at day 10
- 2. To compare the proportion of participants who are asymptomatic and symptomatic at day 10
- 3. To compare the time of onset and frequency of the development of fever and other symptoms of COVID-19 in those who were asymptomatic at enrollment
- 4. To compare the progression in severity of COVID-19 symptoms (hospitalization and length of stay; admission to intensive care unit and number of days in unit; intubation, Death (any cause))
- 5. To compare the severity of disease in participants who develop symptoms of COVID-19
- 6. To compare the side effects of NTZ, RBV + HCQ compared to placebo
- 7. To determine whether baseline viral load predicts response to therapy
- 8. To assess the rate of decline in viral load over days 3 and 6 after randomization
- 9. To assess new, self-reported COVID-19 infection in household members

B. Hypotheses / Research Question(s)

We hypothesize that treatment with NTZ, RBV + HCQ decreases viral load and the progression of symptoms, or emergence of symptoms in those who are asymptomatic at baseline, in SARS-CoV-2-positive adults compared to placebo.

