1.3 Research Design and Methods

We will conduct a randomized clinical trial enrolling eligible participants who are determined to be SARS-CoV-2-positive (e.g., via Rutgers Corona Cohort [RCC] study, hospital or other screening programs) who volunteer for the study. Specifically, we will enroll 70 participants whose test has been performed within the past 7 days who are either asymptomatic or mildly symptomatic at baseline. Mild COVID-19 symptoms include new cough, sore throat, fever, myalgias, new vomiting or diarrheaor change in smell or taste. Illness requiring hospitalization, or those who present with hypoxia (PO2<92%) or shortness of breath at time of enrollment will be classified as significantly symptomatic and excluded from study participation. People who are allergic or intolerant to NTZ, RBV or HCQ will be excluded. We will randomly allocate participants stratified by presence of mild symptoms to 1) NTZ, RBV and HCQ or 2) placebo. Treatment with the investigational agents or placebo will continue for 5 days. Viral load will be assessed at baseline (day 0) as well as at days 3, 6, and 10 to monitor response to antiviral treatment. Immune status will be determined by antibody testing of blood collected at baseline and day 28.

Prior to initiating enrollment, we will prepare two randomization tables for treatment assignment using permuted blocks of six which will be provided to the research pharmacist. One table will be used for participants without symptoms and the other will be used for those with mild symptoms. The pharmacist will prepare kits containing the 5-day supply of study medications (investigational drugs/placebo) which will be sequentially numbered in accordance with the randomization tables. The contents of each kit (investigation drugs/placebo) will be indistinguishable. Study staff will establish symptom status at the baseline visit, and per pharmacy order, provide the participant the next numbered medication kit in the participant's stratum (no symptoms/mild symptoms). The study investigators, staff interacting with the participants are all masked to treatment assignment

A. Research Procedures

- 1. Study Procedures:
 - Day 0/1 Screening/Baseline Visit (in person)
 - Pre-screen via online screening form to confirm eligibility
 - Obtain informed consent for trial enrollment
 - Medical history
 - Medication history
 - Document symptoms (if any)

- o Take temperature, PO2, Pulse
- Q-T interval assessment

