- 4. Proportion of participants with progression of severity of COVID-19 symptoms (hospitalization and length of stay; admission to intensive care unit and number of days in unit; Intubation; Death (any cause))
- 5. Comparison of severity of disease in participants who develop symptoms of COVID-19 at all timepoints
- 6. Assessment of medication toxicity as measured by standard metrics
- 7. Q-T interval from baseline of > 60msec or QT > 500 msec)
- 8. Number of participants with undetectable viral load and absence of symptoms
- 9. Rate of decline in viral load at study days 3 and 6
- 10. New, self-reported COVID infection in household members

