1.9 Data Collection

A. Primary Data Collection

Data collection will occur at a baseline visit with follow-up data collected over the subsequent month as described below.

Location: Study site visits (baseline, day 14 & day 28) will take place at the designated RWJMS study location at [name] which is an Institutional Biosafety Committee (IBC) approved location to meet with SARS-Cov-2 positive individuals. Consent and all questionnaires will be completed electronically online. This questionnaire will include items on health and medical history, lifestyle, employment and patient contact, and demographics. At baseline, contact information (e-mail/phone) for the participant will be collected as well as contact information of 2 individuals who know the participant well who we can reach out to in case the participant falls ill.

Follow-up questionnaires will be administered daily for 10 days and on day 28 after entering the study. Follow-up questionnaires will include items on symptoms of COVID-19, reactions to the study medications and health status of household members since the last questionnaire Up to 3 daily automated reminders will be sent to remind participants to complete the surveys. In addition, participants will self-report their body temperature, PO2, and pulse daily through REDcap, daily for the first 10 days of the study period. Participants will receive automated email/text reminders to record this information daily. We will also call on days 3, 6 and 10 to confirm self specimen collection, check medical status and study drug dosing (on days 3 & 6) and questionnaire completion compliance. On day 14 participants will return for a blood draw and to return the ZIO AT monitoring device. On day 28, participants will return to the clinic for a final symptom assessment, a blood draw for immune function and CBC, pregnancy test, if applicable and final study drug accountability.

- Process of Data Collection: All in-person data collection will be overseen by the clinical study coordinator team conducting study visits, with questionnaires self-administered by participants. The blood specimens will be collected at the in-person visits (baseline, day 14 & 28). Participants will be responsible for reporting their own daily temperatures, PO2 and pulse.

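### Endpoint 4 counts progression only from hospital admission upward, so new hypoxia or shortness of breath at home in the mild stratum has no defined progression measure (minor)

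*Combined protocol and SAP*

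**What the plan says.** Section 1.1 B hypothesizes that treatment "decreases viral load and the progression of symptoms, or emergence of symptoms in those who are asymptomatic at baseline". It thus names two clinical effects: less worsening of existing symptoms and less emergence of new ones.

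- **Progression.** Secondary objective 4 in 1.1 A is "To compare the progression in severity of COVID-19 symptoms (hospitalization and length of stay; admission to intensive care unit", followed by ICU days, intubation and death from any cause. Endpoint 4 in 1.3 F, "Proportion of participants with progression of severity of COVID-19 symptoms (hospitalization and length of stay; admission to intensive care unit", continues with the same list.
- **Emergence.** Endpoint 3 begins "For those who were asymptomatic at baseline: Progression to symptoms" and lists key symptoms. Shortness of breath is among them; PO2 is not.
- **Severity.** Endpoint 5 is "Comparison of severity of disease in participants who develop symptoms of COVID-19 at all timepoints". It gives no scale or threshold.
- **Entry boundary.** Section 1.3 states: "Illness requiring hospitalization, or those who present with hypoxia (PO2<92%) or shortness of breath at time of enrollment will be classified as significantly symptomatic". Such people are excluded, so any later occurrence is new.
- **Data collected.** Section 1.9 A states that "participants will self-report their body temperature, PO2, and pulse daily through REDcap, daily for the first 10 days of the study period". Symptom questionnaires run daily for 10 days and again on day 28.
- **Analysis.** Section 6.1 plans logistic regression with odds ratios and 95% confidence intervals for binary outcomes. Its examples are progression to symptoms, intubation, death, hospitalization and ICU admission.

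**The concern.** Emergence of symptoms has a defined endpoint. Progression has one only at the severe end, and in outpatients with no or mild symptoms that end may produce few events. A mildly ill participant who crosses the protocol's own entry boundary while at home has worsened clinically, and the information to see it is already scheduled. Without a definition fixed in advance, any account of lesser worsening would rest on one chosen after the data are seen.

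A second problem follows from the same sparseness. For the severe outcomes, the odds ratio promised in 6.1 may not be estimable.

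**Working it through.** **Step 1. Which endpoint counts new PO2<92% or shortness of breath, without admission, in someone symptomatic at entry?**

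- Endpoint 3: no, because it is limited to those asymptomatic at baseline.
- Endpoint 4: no, because it starts at admission.
- Endpoint 5: possibly, but severity is undefined, and it is unclear whether people already symptomatic count as developing symptoms.
- Endpoints 2 and 8: these record only absence of symptoms (8 jointly with undetectable virus), so a lingering cough and new hypoxia count alike.
- Adverse events: grade 3 or higher only (1.3 C), and these are safety data.

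No endpoint uses PO2. In the asymptomatic stratum, too, a low PO2 without a key symptom is not counted.

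**Step 2. Inputs.** The documents give 35 per arm (1.5) and 10 daily readings and questionnaires plus day 28 (1.9 A). They give no clinical event rates and no stratum sizes, and there is no stated figure for endpoint 4 to reproduce. All rates below are assumptions, as is a mild stratum of half the trial (35/2, rounded to 18 per arm).

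**Step 3. Empty arms under 6.1.** P(at least one arm without an event) = 1 − [1 − (1−p1)^n][1 − (1−p2)^n]. With n = 35 and equal rates:

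- 1%: 0.99^35 = 0.703; 1 − 0.297² = 0.91
- 3%: 0.97^35 = 0.344; 1 − 0.656² = 0.57

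With one arm empty, the maximum-likelihood log odds ratio is infinite.

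**Step 4. What the extra category could show.** Same formula, n = 18, category or worse, active rate half of placebo:

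| Placebo rate | Expected events, placebo vs active | At least one arm empty |
|---|---|---|
| 20% | 3.6 vs 1.8 | 17% |
| 10% | 1.8 vs 0.9 | 49% |
| 5% | 0.90 vs 0.45 | 78% |
| 3% | 0.54 vs 0.27 | 90% |

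Admissions alone at 3%, halved on active, also give 90%. If the category is as rare as admission, nothing is gained.

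**Step 5. Precision.** Normal-approximation power for a halving (two-sided 0.05, placebo 3% to 20%) is 5% to 13% at 18 per arm and 6% to 21% at 35. An observed 2/18 vs 1/18 is a difference of 5.6%, with an exact unconditional 95% CI of about −18% to 29%.

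**Step 6. Why occurrences must be confirmed.** Let f = 0.5% to 2% be the false-positive chance per report.

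- *Low PO2, any of 10 readings:* 1 − (1−f)^10 = 4.9% to 18%. Two consecutive lows give 0.02% to 0.35% if errors are independent. If a false low repeats next day with probability r = 0.3 to 0.5 (two-state chain, chance of a new low f(1−r)/(1−f)), the result is 1.0% to 4.9%.
- *Shortness of breath, any of 11 questionnaires:* g = 1 − (1−f)^11 = 5.4% to 20%. With true rates of 10% vs 5%, the observed rates are 0.10 + 0.90g and 0.05 + 0.95g. At g = 0.0536 these are 0.148 and 0.101: ratio 0.68, with 0.048/0.148 = 33% of placebo cases false. At g = 0.199 they are 0.279 and 0.239: ratio 0.86, with 0.179/0.279 = 64% false. A true ratio of 0.50 is largely hidden.
- *Shortness of breath on at least two of 10 daily questionnaires:* g = 1 − (1−f)^10 − 10f(1−f)^9 = 0.11% to 1.6% if errors are independent, and the same observed-rate formulas give a ratio of 0.51 to 0.57. With the repeating errors above, g is 1.0% to 5.1% and the ratio 0.55 to 0.67. The repeat rule helps, but does not remove persistent misreporting.

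**The case against.** The strongest objection is endpoint 5. A protocol may reserve progression for hard events and treat milder worsening as severity, and endpoint 5 covers all timepoints. On that reading lesser worsening has a place, and what remains is that its severity is undefined. This stands in part and narrows the point. A reader might infer that the trial can see worsening in the mild stratum only through admission or worse. The documents do not support that: endpoint 5 may cover it, endpoints 2 and 8 show whether symptoms persist, grade 3 or higher adverse events are recorded, and records are reviewed for those who develop symptoms or seek care (1.9 B). None of these, however, is a defined progression measure.

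A reader might also infer from the list in 1.3 D headed "Data Points to be collected" that PO2 was dropped, since it is not there. Pulse and QT are missing from it too, while the schedule of events and 1.9 A provide for PO2. The list is simply not exhaustive, and nothing follows from it.

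The questionnaires are not in the documents, so a severity grade may exist there. The objection that power is too low for a useful comparison is correct, and is why no test is proposed.

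**Conclusion.** The gap is real but narrow: non-admitted new hypoxia or shortness of breath in the mild stratum has no defined progression measure, although the hypothesis names progression and the data are already scheduled. How much a new category would add cannot be established, since every clinical rate and the stratum split are assumed. Two readings go too far. First, 1.3 does not supply a ready intermediate tier: it puts illness requiring hospitalization, hypoxia and shortness of breath in one class, so it offers a threshold only. Second, the new category should not double as the scale for endpoint 5: that would duplicate endpoint 4 and remove any grading among the mildly ill.

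The estimability problem in 6.1 is the firmer part. At assumed equal rates of 1% to 3% it arises 91% to 57% of the time at 35 per arm. Overall this is a minor, optional improvement. The primary endpoint, sample size and primary power are unchanged.

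**What to change.** 1. In objective 4 and endpoint 4, add one descriptive category below hospitalization: not admitted, with PO2<92% on two consecutive available daily home readings (days 1–10), or shortness of breath on at least two daily questionnaires. List single low readings and single reports separately, including a day 28 report, and keep them out of the headline count. Report counts by arm and symptom stratum, with an exact 95% CI for the risk difference in this category or worse. Claim no test.
2. In 6.1, for hospitalization, ICU admission, intubation and death, report counts and exact risk-difference intervals instead of logistic odds ratios when an arm has no event.

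The cost is wording in 1.1 A, 1.3 F and 6.1, plus one questionnaire item if shortness of breath is not already asked. No visit or device is added. Downsides: home PO2 is noisy and stops at day 10; device errors may repeat within a participant; the two-reading rule can miss a single true dip; shortness of breath is subjective and overlaps endpoint 3 in the asymptomatic stratum; and power for any difference between arms is very low.
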